### Methods to Protect Confidentiality

*Describe the data management plan and the methods you will employ to protect subject privacy and the confidentiality of research data. The section should detail how information will be collected, recorded, coded, stored, transmitted, and as applicable, shared with other investigators so as to minimize risks related to breach of confidentiality. Confirm that identifiers are removed, to the extent possible, from research data, and explain if there are links between subject identity and research data, or if the data are anonymous. Also, indicate where the data are stored, who is responsible for data safekeeping, and who has access to subject identity and codes, if any, which cross-link research data and subject identity. Confirm that identifiable data are not collected, stored, or transmitted by mail, fax, on removable drives, laptops, or via the internet without proper protections, e.g. encryption.*

Confidentiality will be maintained by keeping physical data in locked file cabinets. Any electronic data, including laboratory results will be communicated within strict HIPAA rules. Methods by which confidentiality is protected include HIPAA-compliant videoconferencing and web-based platforms. Any data sent to the company will include initials, gender, marital status, SES and education and date of birth only without additional potential identifying information. Should it become necessary for the treating psychiatrist to contact the subject's primary physician to obtain copies of their medical records or release our records to other providers, explicit written agreement for such record transfers will be obtained from the patient. Any electronic data stored at the Anxiety Disorders Clinic will be kept behind the NYSPI firewall with access only to authorized personnel by individual password. We will be applying for a certificate of confidentiality.

We will provide Compass with safety data from the Study, for storage by Compass on a central database. Such information shall be provided to Compass on a regular and on-going basis throughout the Study. Notwithstanding the foregoing, patients must be consented to have their data stored in this secure centralised database, maintained by Worldwide Clinical Trials (WCT). Only patients who consent to this process will have their personal data transferred.

All types of adverse event will be promptly reported to Compass for use in the Compass/WCT safety database, they do however have different recording and reporting requirements, as set out below. For the purposes of reporting to the safety database, and subject to data protection requirements, we will promptly report to Compass all Serious Adverse Events (“SAEs”) regardless of the causal relationship to the Study Drug.

### Assessment of Seriousness

For the purposes of the reporting of the adverse events to Compass, each adverse event will be assessed for its seriousness. An SAE is any event that meets any of the following criteria:

- Death
- Life-threatening
- Inpatient hospitalization or prolongation of existing hospitalization
- Persistent or significant disability/incapacity
- Congenital anomaly/birth defect in the offspring of a subject who received the study drug.

Other: Important medical events that may not result in death, be life-threatening, or require hospitalisation, may be considered an SAE when, based upon appropriate medical judgment, they may jeopardise the Subject and may require medical or surgical intervention to prevent one of the outcomes listed in this definition.

Examples of such events are:

- Intensive treatment in an emergency room or at home for allergic bronchospasm
- Blood dyscrasias or convulsions that do not result in inpatient hospitalisation
- Development of drug dependency or drug abuse

### Adverse Events of Special Interest

For the purposes of the safety database, an adverse event of special interest (“AESI”) is an adverse event (serious or non-serious) of scientific and medical concern specific to the study drug, for which ongoing monitoring by the Clinical Investigator is required. Such adverse events may require further investigation to characterise and understand them.

---

The following events will be reported as AESI:

- Euphoric mood
- Dissociative disorder
- Hallucination
- Psychotic disorder
- Cognitive disorder
- Disturbance in attention
- Mood altered
- Psychomotor skills impaired
- Inappropriate affect
- Overdose
- Intentional product misuse

All AESIs will be followed until resolved or stable.

### Reporting Adverse Events

Each adverse event will be assessed to determine whether it should be classified as a SAE. If the adverse event is considered serious, we will report this event in line with requirements of the study sponsor and the IRB. This may include completing a sponsor specific SAE reporting form, within 24 hours of learning about the event, regardless of causal relationship to the Study Drug.

For the purposes of reporting to the safety database, these events will also be recorded on a specific Compass adverse event database CRF, within 24 hours of our becoming aware of them. This will also be the case for AESI.

If we detect an SAE in a Subject after the last scheduled follow-up visit, and consider the SAE related or possibly related to the administration of the Study Drug, will report this to the sponsor. We will also report the event, on the Compass adverse event database CRF and send this in accordingly.

We will report all other adverse events promptly to the Compass safety database after first becoming aware of such adverse event. These events will be reported and transferred on our Institution's own study CRFs.

All information about adverse events will be collected and once the relevant form is completed, it will be scanned and sent by email message or facsimile to WCT. The initial report should include the following information:

- Event

- Study code
- Reporter name and contact information

Site staff will complete the paper Compass AE Database CRF form and email it to the following address:  
[[contact]](mailto:[contact])

In cases where the email system is unavailable, site staff will send the SAE by fax to: [name] (US) and [contact] (ROW).

Category of Adverse Event	Time Frame to Report to Compass/WCT Database	How to Report to Compass/WCT Database
Adverse Event (AE)	Timely Manner/ Before the end of the study	Submit site specific AE CRF to WCT
Serious Adverse Event (SAE)	Within 24 hours of becoming aware of event	Submit a copy of the Compass provided AE CRF to WCT
Adverse Events of Special Interest (AESI)	Within 24 hours of becoming aware of the event	Submit a copy of the Compass provided AE CRF to WCT

Fig 1. Reporting requirements

Due to the limited safety data that have been collected formally for the Study Drug, all SAEs that are considered to be related will also be unexpected and therefore classified as Serious, Unexpected, Suspected Adverse Reactions (SUSARs). Classification of an SAE as a SUSAR will be determined on a case by case basis by WCT. Once an unexpected event has occurred, it will become expected in the future. The IBD will be updated annually to reflect changes in expected adverse events.

### GDPR

As owners of the external safety database, Compass Pathways are the “data controller” for this aspect of the research. WCT and the research team will act as “data processors”.

Subjects will have the following rights regarding accessing their data stored in this database:

1. To request to review their data held in the safety database.

2. To request for any inaccuracies to be corrected.
3. To raise objections to its content and to the continued processing of their data in this database.
4. To request to have their data removed from this database.

If any subject requests any of the above points regarding their safety data held in the safety database, we will notify Compass as soon as the request is made. Requests will be reviewed on a case-by-case basis and where Compass sees fit to action the request; they will work with us to resolve them as needed.

### Direct Benefits to Subjects

*Describe only benefits to individual subjects that are likely to accrue during the study itself. Do not include subject compensation or treatment to be provided at the end of the study, as these do not figure into the IRB's risk/benefit considerations. Do not describe diagnostic and evaluation components unless subjects receive clinical feedback. Do not describe the anticipated scientific benefits of the research. Some studies offer no direct benefit to subjects.*

There may be no direct benefit. The information we get from this study may help us treat people with BDD better in the future

### Compensation and/or Reimbursement

*If compensation or reimbursement for expenses will be offered to subjects, please describe and indicate total amount and schedule of payment(s). If transportation is reimbursed, state if receipts are necessary for reimbursement. Include justification for compensation amounts and indicate if there are bonus payments.*

\$300 after completion of the pre-dosing visit, dosing visit, and the post dosing visit (\$100 each visit).

\$250 after completion after completion of 5 follow up visits. (\$50 each visit)

Total compensation will be \$550

### Protocol Specific Plans (PSPs)

*All federally funded, more than minimal risk studies are required to include a Training Plan, an Internal Monitoring/Quality Assurance Plan, and a Data Management Plan. Collectively, these plans are called the Protocol Specific Plans or PSPs. More information can be found on the IRB website ([irb.nyspi.org](http://irb.nyspi.org)) regarding these plans and should be reviewed prior to submission.*

### Training Plans

A training plan should describe, in detail, ALL training required for each member of the study team, frequency of the training, and location of the Training Log and training certificates. Elements of an effective training plan include: all sessions documented with an attendance list, all members of the study team listed on the Delegation of Authority log must be in compliance with the training plan and be trained for each study procedure they are authorized to perform, the training log is maintained by the Research Coordinator in the Regulatory Binder, and sample timepoints for the Training Log are before protocol initiation meeting, protocol initiation meeting, annual protocol meeting, and new staff training. The study is in data analysis and is not currently enrolling or recruiting participant so this would not be applicable to us.

### Internal Monitoring/Quality Assurance Plan

Please utilize the Quality Assurance Monitoring plan template on the NYSPI IRB website ([irb.nyspi.org](http://irb.nyspi.org)) and cut & paste to this section. A lead QA monitor will need to be designated and named in the study's monitoring plan. Section A will describe the monitoring schedule and reporting. Section B will describe the data that will be reviewed on an ongoing basis. The study is in data analysis and is not currently enrolling or recruiting participant so this would not be applicable to us.

### Data Management Plan

The required elements of the Data Management Plan include: identification of the database platform (e.g., REDCap) and inclusion of an attestation that it is Part 11 compliant, identification of a qualified staff member who designs and maintains the database, design and implementation of data system training for all Principal Investigators & research coordinators & all protocol staff, and significant changes to the data management plan will be submitted as protocol amendments in PRISM. The study is in data analysis and is not currently enrolling or recruiting participant so this would not be applicable to us.

## **Statistical Analysis Plan**

The primary efficacy measure was BDD symptom severity, as measured by the BDD-YBOCS, a clinician-rated scale (total score range: 0-48, with higher scores indicating greater severity). Response to treatment has been defined and validated as  $\geq 30\%$  decrease in total score, and partial-to-full remission as total score  $\leq 16$  (Fernandez de la Cruz et al. 2019).

**Statistical Analyses:** For YBOCS and other repeated outcome measures, repeated measures ANOVAs with Greenhouse-Geiser corrections will be conducted across time points from baseline to week 12 using SPSS Version 23.0 (IBM SPSS Statistics for Windows, Version 23.0. Armonk, NY: IBM Corp), with post hoc pairwise Bonferroni-corrected comparisons. For the HRSD a paired samples *t*-test will be performed to compare baseline to week 12 scores.

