### Summary of Experiences to Date

**Please provide a summary of scientific progress of the study and the experience of research participants, to date. This requirement is designed to allow for the investigator and the IRB to reassess the study's risks and benefits in terms of developments in the field, changing practice patterns, and new IRB policies and procedures.**

The study has concluded and is in the data analysis stage. Recruitment is closed and subject follow-ups have been completed. A total of 12 participants were enrolled in the study with 5 participants enrolling in the past year. None of the participants were withdrawn from the study or discontinued. There are no Serious Adverse Events to report.

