### Lay Summary of Proposed Research

*This section is intended to provide a basic overview of the study including a description of its purpose, study procedures, and subject population. The summary should provide a concise overview of the study for non-scientific and scientific members of the IRB. Please avoid medical or technical terminology. In general, the abstract of a grant does not provide a suitable lay summary.*

Body dysmorphic disorder is a common condition characterized by symptoms of "imagined ugliness" with debilitating distress, checking and avoidance behaviors, and seeking unnecessary cosmetic medical procedures. Serotonin reuptake inhibitor medications and cognitive behavioral therapy helps some patients, but many do not benefit from existing treatments, and no medications are FDA-approved for this indication. Psilocybin is under development as a treatment of several psychiatric disorders, with placebo-controlled trial evidence of safety and prolonged efficacy for major depression when administered as a single dose with intensive support by a therapist on the day of administration. A single case report in body dysmorphic disorder suggests psilocybin might also have efficacy for this disorder.

In this proposed pilot study, up to 12 adults with body dysmorphic disorder that has not responded to at least one adequate trial of a serotonin reuptake inhibitor will be treated openly with a single oral dose of psilocybin. Procedures will follow those previously established in depression studies of psilocybin. Patients will receive intensive preparation and support from two therapists, including 8-9 hours accompanying the patient on the day of medication administration in the Biological Studies Unit. Follow-up visits to monitor safety and clinical outcome will be conducted at day 1, week 1, and months 1, 2, and 3 post-administration. Resting state MRI will be conducted prior to and one day after psilocybin administration to assess the effect of medication on brain circuits.

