**Specific Aims and Hypotheses**

*Concisely state the objectives of the study and the hypothesis or primary research question(s) being examined. There should be one hypothesis for every major study procedure or intervention. For pilot studies, it is important not to overstate the study's objectives. If there are no study hypotheses, describe broad study goals/aims.*

1. Psilocybin will be acceptable to, and safe and well tolerated by, patients with BDD
2. Symptoms of BDD will improve after psilocybin administration, with persistent improvement over 3 months of follow up
3. Resting state functional connectivity of the default mode network will increase from pre- to post-treatment

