**Detailed Procedure for Staff Escort Home**

In the event that it is deemed appropriate for a patient to return home following their psilocybin experience and said patient has not provided a responsible party to accompany him or her home, a staff member will accompany the individual from the BSU treatment room to the exterior door of their home. Transportation will be via a car service for which we will pay. The staff member will be instructed to contact the Anxiety Disorders Clinic doctor on call should he or she note grogginess or unsteady gait or other reasons to think the subject might have trouble being alone and the doctor will determine whether to have the staff member bring the subject back to NYSPI for further observation, erring on the side of further observation. Else, the staff member will allow the individual to enter their home and close the door, the staff member remaining outside and relieved of escort duties.

Table - Schedule of Study Procedures											
Visit	1	1a, 1b, 1c, etc.	2	3	4	5	6	7	8	9	10
Day	Screen Visit	Screening Period	-1	Psilo-cybin	+1	+7	+14	+21	+42	+63	+84
Informed Consent	X										
Medical History	X		X								
MINI Interview	X										
Documentation of Birth Control Method	X										
Prior/Concomitant Meds	X	X	X	X	X	X	X	X	X	X	X
Hamilton Rating Scale for Depression	X		X		x				x		X
Columbia Suicide Severity Rating Scale	X				x						x
BDD-Yale-Brown OCD Scale	X		X	X	X	X	X	X	X	X	X

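### Minor, cheap improvement: Holm's step-down procedure could replace single-step Bonferroni for the post hoc pairwise comparisons, with the same error control and equal or greater power

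*Combined protocol and SAP*

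**What the plan says.** The SAP opens with "The primary efficacy measure was BDD symptom severity, as measured by the BDD-YBOCS". For this scale and the other repeated outcomes, "repeated measures ANOVAs with Greenhouse-Geiser corrections will be conducted across time points from baseline to week 12", "with post hoc pairwise Bonferroni-corrected comparisons". The HRSD (Hamilton depression scale) is handled separately, by one paired t-test of baseline against week 12.

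The SAP gives no alpha, power target, effect size or SD. It does not list the comparisons or say whether they are all pairs or only comparisons with baseline.

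The efficacy hypothesis under Specific Aims and Hypotheses is "Symptoms of BDD will improve after psilocybin administration, with persistent improvement over 3 months of follow up". The Lay Summary describes "In this proposed pilot study, up to 12 adults with body dysmorphic disorder", treated openly. The continuation section reports that "A total of 12 participants were enrolled in the study", that all interventions are finished, and that only data analysis is ongoing.

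**The concern.** An omnibus ANOVA over time shows that the mean score changed somewhere. It does not show that Week 12 differs from baseline. For the BDD-YBOCS, only the adjusted pairwise comparisons in the SAP address the persistence part of the hypothesis.

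With 12 patients and a scale rated at many visits, the per-comparison threshold is strict. Single-step Bonferroni holds every comparison to that threshold, however many others have already been rejected. Holm relaxes it after each rejection. If several visits improve together, as the hypothesis expects, the weaker late contrasts can benefit. At stake is some power for those contrasts.

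**Working it through.** **Inputs from the documents.** Twelve patients, all completed. In the Schedule of Study Procedures, the row "BDD-Yale-Brown OCD Scale" is marked at screening, Day -1, the dosing day, and Days +1, +7, +14, +21, +42, +63 and +84. Day -1 to Day +84 is nine time points.

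**Assumed, because the documents do not say.** Two-sided family-wise alpha 0.05, normal scores, equal correlation 0.5 between visits, dosing-day score unchanged from Day -1, and a Week 12 change of 1.0 SD. At correlation 0.5 the SD of a change is √(2 × (1 − 0.5)) = 1 times the SD of a score, so the two scales coincide. The plan states no figure to reproduce.

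**Family size m.** All pairs: 9 × 8 / 2 = 36 (28 if the dosing day is left out). Comparisons with baseline only: 8 (or 7).

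**Thresholds.** Bonferroni tests every pair at 0.05/m: 0.05/36 = 0.00139 (critical |t| on 11 df 4.24) or 0.05/8 = 0.00625 (critical |t| 3.37). Holm orders the p-values, compares them with 0.05/m, 0.05/(m−1), …, 0.05/1, and stops at the first non-rejection.

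**Why Holm never loses a rejection.** Each Holm threshold is at least 0.05/m. If a p-value is at or below 0.05/m, so are all smaller ones, and Holm therefore reaches it and rejects it.

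**Why the error control is the same.** With m₀ true null hypotheses, a false rejection requires some true-null p-value at or below 0.05/m₀. The probability of that is at most m₀ × 0.05/m₀ = 0.05 under any correlation.

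**Why the chance of any rejection is the same.** Both procedures use 0.05/m for the smallest p-value.

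**Bonferroni power, analytic check.** The noncentrality is 1.0 × √12 = 3.46 on 11 df. This gives power 0.31 at |t| > 4.24 and 0.56 at |t| > 3.37.

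**Simulated power for baseline versus Week 12** (change 1.0 SD; Monte Carlo error about 1 point; ranges span separate runs):

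| Family | Course after dosing | Bonferroni | Holm |
|---|---|---|---|
| All 36 pairs | flat | about 31% | 32-33% |
| All 36 pairs | waning from 1.4 to 1.0 SD | about 31% | about 35% |
| 8 versus baseline | flat | 55-58% | 66-70% |
| 8 versus baseline | waning from 1.4 to 1.0 SD | about 56% | 74-75% |

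In the 36-pair family, Holm found at least one extra difference somewhere in about 24% (flat) to 39% (waning) of trials. No Bonferroni rejection was lost in any run.

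**Why the family decides the size.** In the flat case 14 of the 36 pairs truly differ: two unchanged time points, each against seven later visits. After 13 rejections the Holm threshold is still only 0.05/23 = 0.0022. In the family of eight, after six rejections it is 0.05/2 = 0.025.

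**Other effect sizes** (correlation 0.5, same change at every time point after Day -1, including the dosing day; Bonferroni to Holm):

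| Change | 36 pairs | 8 versus baseline |
|---|---|---|
| 0.5 SD | 2.9% to 2.9% | 10.7% to 12.9% |
| 0.8 SD | 15.4% to 15.9% | 35.4% to 46.4% |
| 1.0 SD | 31.7% to 33.0% | 54.3% to 70.1% |
| 1.5 SD | 78.8% to 80.8% | 94.0% to 99.2% |
| 2.0 SD | 97.8% to 98.4% | 99.9% to 100% |

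With the dosing day unchanged, the 36-pair gain at 1.5 SD is somewhat larger, about 4 to 6 points.

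**The case against.** A reader might infer that the trial gives up power for nothing. The documents do not support that, for three reasons.

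- **Intervals.** Bonferroni directly supplies simultaneous confidence intervals for the mean changes, and Holm has no comparably simple ones. In a small open pilot, intervals may be worth more than a few extra rejections. This stands as a real cost. It is limited by the fact that the SAP plans no confidence intervals, so no planned output is lost.
- **Family.** The larger gains need a baseline-only family that the SAP never states. After an omnibus ANOVA, pairwise most naturally means all pairs, and there the Week 12 gain is small. This stands.
- **Reach.** The adjustment touches only the post hoc comparisons, and no decision rule or power target rests on them. This also stands.

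It is also fair to say that defining the family matters more. Under plain Bonferroni, going from 36 pairs to 8 raises power at 1.0 SD from about 31% to about 55%, far more than Holm adds within 36. That is a separate, compatible change, since Holm applies to whichever family is used.

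Finally, moving to a more permissive procedure once the study is in data analysis, in an open-label trial, is not a mere edit. The fix has to deal with this.

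**Conclusion.** This is a minor, optional efficiency gain. Bonferroni is valid and nothing in the plan is wrong. Holm's advantage in the tests is certain in direction: the same family-wise error control, no rejection lost, and sometimes more gained.

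Its size is not fixed by the documents. At 1.0 SD under the stated assumptions it is about 2 to 4 points for Week 12 in the all-pairs family, and about 11 to 19 points if only the eight baseline comparisons are made. It shrinks towards nothing when effects are small or very large.

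The stronger reading, that the choice of Bonferroni is a main limit on what this trial can show, would need both a mid-range effect and the short family. The documents state neither.

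**What to change.** In the SAP's Statistical Analyses paragraph, replace "post hoc pairwise Bonferroni-corrected comparisons" with: post hoc pairwise comparisons adjusted by the Holm step-down procedure. Apply it to the same family of pairs that Bonferroni would have had. In practice, take the unadjusted paired p-values from SPSS, sort them, compare them with 0.05/m, 0.05/(m−1) and so on, and stop at the first non-rejection.

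Make the change as a dated SAP amendment that says whether outcome data had been examined. If they had, keep Bonferroni as the planned result and show Holm beside it, labelled post hoc.

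The cost is one phrase, a sorting step and the amendment. Holm brings no simple matching simultaneous intervals, so label any 95% intervals as unadjusted or Bonferroni-adjusted. Unadjusted intervals may exclude zero where Holm does not reject.

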## Protocol Summary Form

Inclusion:	
1. Age 18-55	Date of birth
2. DSM-5- body dysmorphic disorder, non-delusional subtype, for >6 months by history. Non-delusional subtype will be operationalized by Brown Assessment of Beliefs Scale (BABS) 6-item total <18 (Phillips et al., 2006)	SCID -5 BDD module, BABS
3. At least moderate severity of BDD, operationalized by total score >24 on the Yale-Brown Obsessive-Compulsive Scale Modified for Body Dysmorphic Disorder (BDD-YBOCS),	BDD-YBOCS
4. At least moderate overall severity, operationalized by score of at least moderate (4 or greater) on the CGI severity scale	CGI severity scale
5. History of intolerance of, or nonresponse to, a prior adequate trial of an SSRI ( $\geq$ 2 months of fluoxetine 20 mg/day or equivalent), SNRI, or clomipramine	Psychiatric History
6. Currently in psychotherapy (other than CBT for BDD)	Psychiatric History
7. Able to provide informed consent	Psychiatric Assessment
Exclusion:	
1. Current major depressive disorder of greater than moderate severity (17-item Hamilton Rating Scale for Depression total >20)	Hamilton Rating Scale for Depression

2. Current or past DSM-5 bipolar disorder, psychotic disorder, or borderline personality disorder. First degree relative with psychotic disorder or bipolar I disorder.	MINI, family history
3. DSM-5 alcohol or drug use disorder in the past 3 months, or positive result on urine drug screen for illicit substance of abuse (except that prior cannabis use subthreshold for abuse diagnosis will be permitted if discontinued >24 hours prior to dosing)	MINI, urine drug screen
4. Current clinically significant suicidality or a suicide attempt within the past year	Psychiatric Assessment, MINI, CSSR (items 3 or 4 rated “yes” for active suicidal ideation)
5. Need for inpatient or partial hospital treatment	Psychiatric Assessment
6. Mental retardation, dementia, brain damage, or other cognitive impairment that would interfere with participation	Psychiatric Assessment and History
7. Body image concerns accounted for primarily by an eating disorder	Psychiatric Assessment
8. Body dysmorphic disorder criteria not met if weight concerns are excluded	Psychiatric Assessment

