chemistries including thyroid function. A physical examination will be performed at the screening or between screening and Visit 2 (Day -1), with results obtained before psilocybin administration day.

Additional screening will specifically assess eligibility for the MRI portion of the study with the self-rated PhenX Toolkit Hand Dominance Measure and MRI Metal Screening Questionnaire. Contraindications to MRI scanning are:

- Paramagnetic metallic implants or devices
- Contraindicating magnetic resonance imaging or any other non-removable paramagnetic metal in the body (e.g., pacemaker, paramagnetic metallic prosthesis, surgical clips, shrapnel, necessity for constant medicinal patch, some tattoos)
- Being unable to tolerate the scanning procedures (i.e., severe obesity, claustrophobia)

Patients with contraindicated metal or left-handedness will not be offered MRI participation but will complete all other parts of the protocol.

Additional visits (V1a, V1b) will be scheduled as needed to follow up on any lab abnormalities and for patient to establish relationship with study therapist.

Participants will be invited to bring to the screening a companion (friend/family member) whom they would like to support them through the study. Such a companion will be informed of their potential role and will be asked to sign a “caregiver” consent form at the Screening Visit. Caregivers will receive information about the signs of worsening of depression and suicide risk and ways to contact the study team if necessary. The caregiver will complete a questionnaire at screening, Week 3 and Week 12.

**2. Visit 2 (Baseline, Day -1).** Eligibility and willingness to participate will be reassessed. At this visit, the patient meets with the therapist who describes what the experience might be like and how the therapist will handle any difficulties the patient may have with the experience. MRI-eligible subjects will complete acquisition of resting state fMRI. Subjects will also complete an inverted face computer task in which they will view an image of a face and then will be shown an image of two faces (one matching and one non-matching morphed face) and asked to select the matching face as rapidly and accurately as possible. The matching and non-matching faces will be presented either upright or inverted, in various combinations. This task assesses global vs. local visual processing, and it has previously been shown to be abnormal in BDD (Feusner, 2010).

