**3. Visit 3 (Psilocybin Day, Day 0).** The next day, a study psychiatrist again assesses eligibility; those eligible and agreeable receive their dose of psilocybin (25 mg) and spend the next eight hours (longer if needed) with the two therapists; when deemed appropriate, the patient is accompanied home either by a person of their choosing or a staff member. The patient will be reminded that they should not drive or drink alcohol at least until after the end of Visit 4 (next day). Vital signs are taken prior to their dose of psilocybin and prior to leaving the clinic and a study psychiatrist evaluates prior to their departure for whether their condition requires them not to leave. In the latter case, they will either remain in the Biological Studies Unit (BSU) until

cleared by a study psychiatrist or admitted to 5-South inpatient service if they require additional observation overnight.

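### Read with the visit schedule, the all-pairs Bonferroni correction on the BDD-YBOCS spans 36 comparisons, of which 7 set baseline against a post-dose day; the rule is valid but costs power at n = 12

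*Combined protocol and SAP*

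**What the plan says.** The Statistical Analysis Plan makes the BDD-YBOCS the primary efficacy measure. For it and the other repeated outcomes, "repeated measures ANOVAs with Greenhouse-Geiser corrections will be conducted across time points from baseline to week 12", "with post hoc pairwise Bonferroni-corrected comparisons". It gives no number of comparisons, no restriction to baseline contrasts, and no alpha, effect size, SD or power. The depression scale, by contrast, gets a single paired t-test of baseline against week 12.

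Study Procedures fixes baseline: "Visit 2 (Baseline, Day -1". In the Table - Schedule of Study Procedures, the row "BDD-Yale-Brown OCD Scale" is marked at screening and then at Day -1, the dosing day, +1, +7, +14, +21, +42, +63 and +84.

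Aim 2, under Specific Aims and Hypotheses, reads: "Symptoms of BDD will improve after psilocybin administration, with persistent improvement over 3 months of follow up".

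**The concern.** Aim 2 asks first whether scores after dosing are below baseline, and then whether they stay there for three months. The omnibus F cannot show that Week 12 is below baseline; the pairwise step has to do that. If the correction covers every pair of visits, the Week 12 contrast is tested at 0.05/36 = 0.0014. Over the baseline contrasts alone it would be tested at 0.05/7 = 0.0071.

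Most of the allowance for error then goes to pairs that are not tests of change from baseline after dosing. In an open pilot of 12 people, a real and lasting improvement could be reported as not significant for that reason alone.

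**Working it through.** The documents state no power or effect size, so there is no figure of the plan's own to reproduce.

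**Inputs**
- Ratings from baseline to week 12: 9 (schedule table, with baseline at Day -1).
- Sample size: 12 enrolled and 12 completed (Application for Continuation of Research).
- Alpha: 0.05 two-sided, assumed.
- Each comparison: a paired t-test on 11 df, assumed.
- Standardised change, dz = mean change / SD of change: assumed, shown over a range.

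**Number of comparisons**

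9 × 8 / 2 = 36 pairs, made up of:
- 7 comparing Day -1 with a day after dosing;
- 8 involving the dosing-day rating;
- 21 comparing two post-dose days (7 × 6 / 2).

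The timing of the dosing-day rating relative to the dose is not given. The text times other measurements that day ("Vital signs are taken prior to their dose of psilocybin and prior to leaving the clinic") but not this scale.

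**Thresholds**
- Over 7: 0.05/7 = 0.00714, critical t = 3.295. Smallest significant observed change = 3.295/√12 = 0.95 SD of change.
- Over 36: 0.05/36 = 0.00139, critical t = 4.240. Smallest significant observed change = 4.240/√12 = 1.22 SD of change.

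**Power for one baseline contrast** (noncentral t, df 11, noncentrality dz × √12)

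| Assumed dz | Over 36 pairs | Over 7 contrasts |
|---|---|---|
| 0.5 | 3% | 11% |
| 0.8 | 15% | 36% |
| 1.0 | 31% | 58% |
| 1.25 | 56% | 82% |
| 1.5 | 79% | 95% |
| 2.0 | 98% | 99.9% |

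**In scale points**

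Inclusion criterion 3 requires a "total score >24 on the Yale-Brown Obsessive-Compulsive Scale Modified for Body Dysmorphic Disorder (BDD-YBOCS"), so the lowest entry score is 25. The plan's response threshold is a 30% fall, and 30% of 25 is 7.5 points. For a true mean fall of 7.5 points and an assumed SD of change of 5 / 6 / 7 / 8 / 10:
- over 36 pairs, power is 79 / 56 / 38 / 25 / 12%;
- over 7, it is 95 / 82 / 66 / 51 / 31%.

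The entry floor is the least favourable case. With an assumed mean baseline of 30, 30% is 9 points, and at SD 7 power is 60% over 36 and 84% over 7.

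**Sensitivity to the count, at dz = 1.0**
- Dosing day left out: 28 pairs, 35%.
- Screening added: 45 pairs, 28%.
- Dosing-day rating counted as post-dose: 8 baseline contrasts, 56%.
- Shorter follow-up in the Lay Summary (day 1, week 1, months 1, 2 and 3): six time points, 15 pairs against 5 baseline contrasts, 45% vs 64%.

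The gap narrows on the shorter schedule but does not close under any of these counts.

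**The case against.** The strongest reply is that nothing here is wrong. All-pairs Bonferroni is valid and conservative. The comparisons are labelled post hoc, they follow an omnibus test that is not itself Bonferroni-corrected, and the study is a small open pilot. That stands: this is a matter of efficiency, not of error control.

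Three stronger readings are tempting, and the documents do not support them.
- A reader might infer that only the seven baseline contrasts bear on Aim 2. The aim includes persistence, and a comparison such as +7 with +84 shows whether an early gain is lost. The seven are the direct test of improvement, not the only relevant pairs.
- A reader might take the drop from 58% to 31% as the loss for a moderate effect. It belongs to an assumed dz of 1.0, conventionally large, and lies near the widest gap. At dz 0.5 power is 11% even over seven contrasts, so the change would not rescue a moderate effect.
- A reader might take 36 as the plan's own number. It is an inference from the schedule, though the natural one, since the table is more detailed than the Lay Summary.

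Two objections concern the remedy. Interventions are complete and only analysis remains, so shrinking the family now makes a positive result easier. That stands and calls for disclosure. Also, a single Day +84 contrast at 0.05 would have 88% power at dz 1.0. That is true, but choosing one visit after collection would loosen the threshold further and drop the formal tests at the earlier days.

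**Conclusion.** The point holds as a cheap gain in efficiency. The plan's correction is valid but wider than the question of change from baseline needs: 36 pairs on the natural reading (28 without the dosing day), of which 7 compare baseline with a day after dosing. For an assumed dz between 0.8 and 1.5, the wider family costs roughly 16 to 27 percentage points of power per contrast. The loss is small in absolute terms at dz 0.5, where both rules have little power, and at dz 2.0, where both have nearly full power.

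This rests on n = 12 with complete data, two-sided 0.05, a paired t-test for each pair, and assumed effect sizes; the documents supply no SD of change. It affects the pairwise step only. It does not show that the plan inflates error, that the omnibus test is impaired, or that the trial could not detect a lasting benefit.

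**What to change.** In the Statistical Analysis Plan, replace the unrestricted pairwise set for the BDD-YBOCS with seven comparisons: Day -1 with +1, +7, +14, +21, +42, +63 and +84, Bonferroni-corrected over seven (0.0071 each). Name Day +84 as the persistence comparison. Present changes between post-dose days, such as +7 to +84, descriptively with means and confidence intervals. State whether the dosing-day rating is taken before or after the dose.

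Because data collection is complete, state whether BDD-YBOCS data had been examined when the change was made, and report both the all-pairs and the seven-contrast adjusted p-values.

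The cost is a few lines of text, with no new data or visits. The seven-contrast family still holds the familywise error at or below 0.05. The downsides are that post-dose pairs, which also bear on persistence, lose their formal test, and that the threshold becomes less strict after collection. Reporting both sets of p-values lets readers see what difference that makes.
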